11.2. ALL

For the ALL patients, the historical data suggested the overall response rate to current standard treatment is 20%. The target response rate would be 40% after the treatment. The trial will be continuously monitored. The study will be stopped early if the data suggest that:

$$\Pr(\pi > 0.2 | \text{data}) < 0.4$$

Here π is the overall response (OR) rate. That is, if at any time during the study we determine that there is a less than 40% chance that the average OR rate is greater than 20%, we will terminate the study. The OR rate is assumed to follow a non-informative prior of Beta (0.4, 1.6). The study will be stopped early if (The number of overall responses)/ (The number of patients evaluated) $\leq 1/8, 2/11, 3/17$.

Table 3: Operating characteristics for monitoring of overall response rate in ALL patients

True Response Rate	Early Stopping Probability	Median Sample size (interquartile)
0.15	0.85	8 (8,11)
0.2	0.7	11 (8, 20)
0.25	0.54	17 (8, 20)
0.3	0.38	20 (8,20)
0.35	0.26	20 (17, 20)
0.4	0.16	20 (20, 20)

Monitoring of non-hematological \geq grade 3 toxicities

With the concern of treatment related toxicity, the non-hematological toxicity (\geq grade 3) throughout all the cycles of treatment will also be closely monitored during the study for AML and ALL together.

Denote the probability of toxicity by P_E . We assume $P_E \sim \text{beta}(0.6, 1.4)$. Our stopping rule is given by the following probability statement: $\Pr(P_E > 0.3 \mid \text{data}) > 0.9$. That is, we will stop the trial if, at any time during the study, we determine that there is more than 90% chance that the toxicity rate is more than 30%. The study will be stopped early if (The number of non-hematological toxicities being grade 3 or higher)/ (The number of patients evaluated) $\geq 7/13, 8/15, 9/18, 10/21, 11/23, 12/26, 13/29, 14/32, 15/35, 16/38, 17/41, 18/43, 19/46, 20/49, 21/52, 22/55, 23/58, 24/61, 25/64, 26/67, 27/70, 28/73, 29/76, 30/79$. The operating characteristics are summarized in table 4.

Table 4: Operating characteristics for monitoring of non-hematological \geq grade 3 toxicities in AML or ALL patients

True Toxicity Rate	Early Stopping Probability	Median Sample size (interquartile)
0.25	0.15	80 (80, 80)
0.3	0.35	80 (27, 80)
0.35	0.63	42 (11, 80)
0.4	0.88	19 (7, 47)

Analysis method

Data analysis will be performed using SAS or S-plus, as appropriate. The proportion of patients having overall response, the mortality rate, and the proportion of patients having grade 3 or higher non-hematological toxicities will be estimated by the corresponding posterior mean and 90% posterior credible interval.

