the combination of clofarabine with cytarabine and anthracycline (CIA regimen). In a phase I study for patients with relapsed/refractory AML, the following doses were established for further evaluation: clofarabine 22.5 mg/m² daily x 5 days, idarubicin 6 mg/m² daily x 3 days, and cytarabine 0.75 mg/m² daily x 5 days.²² In a recent update of a phase II study of 63 patients treated with CIA regimen,²³ the overall response rate was 38% including 21% CR. Median overall survival was 34 weeks for all patients and 66 weeks for those patients who achieved CR/CRp. Twenty-four patients (38%) were able to proceed with a stem cell transplant. Induction mortality was at 8%. Toxicities were manageable.

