5.2. Induction

5.2.1 Phase I (fixed dose of decitabine 20mg/m2 days 1-5, idarubicin 10 mg/m2 days 6-8 and cytarabine 1 g/m2 days 6-10)

Clofarabine 15 mg/m2 IV over approximately 1 hour daily.

Dose levels and dose escalation schema are described below.

Dose level	Clofarabine 15 mg/m2/day IV daily
-1	Clofarabine daily for 3 days (days 6-8)
1	Clofarabine daily for 4 days (days 6-9)

Decitabine 20 mg/m2 IV over approximately 1 hour daily for 5 days (days 1-5)

Idarubicin 10 mg/m2 IV over approximately 30 minutes daily for 3 days (days 6-8)

Cytarabine 1 g/m2 IV over approximately 2 hours daily for 5 days (days 6-10)

Idarubicin will follow clofarabine by 1 to 2 hours and cytarabine will follow clofarabine by 3 to 6 hours. All chemotherapeutic agents will be dosed, prepared, and administered according to MDACC institutional guidelines. BSA will be recalculated prior to each subsequent course.

A DLT is defined as a clinically significant adverse event or abnormal laboratory value assessed as unrelated to disease progression, intercurrent illness, or concomitant medications and occurring during the first course on study that meets any of the following criteria:

- CTCAE Grade 3 total bilirubin or AST (SGOT) or ALT (SGPT) for > 7 days
- CTCAE Grade 4 total bilirubin or AST (SGOT) or ALT (SGPT) of any duration

- All other clinically significant NCI common terminology criteria that are CTCAE Grade 3 or 4

An AE must be clinically significant to define DLT e.g. alopecia, study drug-related fever, electrolyte abnormalities (including K, Na, Cl, HCO₃, Mg, Ca) that are < Grade 3 will not define the DLT. Prolonged myelosuppression, as defined by the NCI criteria specific for leukemia, i.e. marrow cellularity <5% on day 42 or later from start of therapy without evidence of leukemia, will be considered as DLT. All other prolonged myelosuppressions will also be monitored closely. Note: As the patients receive 5-days of decitabine therapy prior to starting the induction chemotherapy, extra 5-days will be allowed to assess for prolonged myelosuppression. In addition to the above, patient death will be monitored closely. Any death will be submitted to discussion by the Department of Leukemia meeting.

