11. STATISTICAL CONSIDERATIONS

Phase I

First, phase I study is performed to assess the safety of different dosing schedules for clofarabine combined with fixed dosage of decitabine, idarubicin, and cytarabine. Two dose schedules are defined in table 1, and the starting dose schedule is dose level 1. A maximum of 18 AML patients will enroll in the phase I study.

Table 1: dose schedule

Dose level	Clofarabine 15 mg/m²/day IV daily
-1	Clofarabine daily for 3 days (days 6-8)
1	Clofarabine daily for 4 days (days 6-9)

Decitabine 20 mg/m² IV over approximately 1 hour daily for 5 days (days 1-5)

Idarubicin 10 mg/m² IV over approximately 30 minutes daily for 3 days (days 6-8)

Cytarabine 1 g/m² IV over approximately 2 hours daily for 5 days (days 6-10)

Dose Escalation Procedures

Starting with Dose level 1, the patient will be enrolled by cohort of 3. Once the DLT assessment for the 3 patients is completed, a sequential of another cohort of 3 patients will be enrolled. If at any time, we see more than 30% patients experiencing DLT, we will deescalate to dose level (-1). If no dose de-escalation occurs, with a total of 18 patients treated at dose level 1, dose level 1 will be considered as the MTD for the phase II part. If there is dose de-escalation, a cohort of 3 patients will be treated, Dose level -1 will be declared as MTD if there are ≤ 1 out of 6 patients experience DLT.

Phase II

Phase II part is a single arm study using the dosage schedule recommended from phase I. A maximum of 60 AML patients which includes 42 new patients and the 18 patients from phase I MTD level, and 20 ALL patients will be enrolled in the study. The trial will be continuously monitored regarding efficacy for each cohort, AML and ALL respectively. The toxicity will be jointly monitored for AML and ALL patients. The method of Thall, Simon, and Estey will be used to perform interim efficacy and safety monitoring.⁵³ The software Multc99.Version 2.1 was used to run the simulation.

Efficacy

The primary endpoint is the overall response which is defined as the best response (either CR, CRp, or CRi) within 56 days.

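### Phase II has no stopping boundary for death: its one numeric safety rule counts a death the same as any grade 3 non-hematological event, under a 30% limit

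*Combined protocol and SAP*

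**What the plan says.** Section 11 applies one toxicity rule to AML and ALL patients together. The trial stops if, at any time, "there is more than 90% chance that the toxicity rate is more than 30" percent. The prior is Beta(0.6, 1.4), and the count is "The number of non-hematological toxicities being grade 3 or higher" over the number of patients evaluated. Events "throughout all the cycles of treatment will also be closely monitored", so there is no separate induction or early window. The population is "A maximum of 60 AML patients which includes 42 new patients and the 18 patients from phase I MTD level, and 20 ALL patients", which makes 80. Table 4 gives early stopping probabilities of 0.15, 0.35, 0.63 and 0.88 at true toxicity rates of 25%, 30%, 35% and 40%.

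On death, the plan has three statements and no phase II boundary:
- Section 2.3, on the earlier CIA study: "Induction mortality was at 8" percent.
- Section 5.2.1 (phase I) says that deaths will be watched and each one taken to a departmental meeting. It gives no threshold, and section 5.2.2 (phase II) has no such text.
- Section 11, Analysis method: "the mortality rate, and the proportion of patients having grade 3 or higher non-hematological toxicities will be estimated" by posterior mean and 90% credible interval. The plan gives neither a time window nor a prior for mortality.

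On aplasia, section 5.2.1 says "marrow cellularity <5% on day 42 or later from start of therapy without evidence of leukemia, will be considered as DLT". This is a hematological event, so the phase II rule does not count it. Section 2.6 enrols ALL patients in phase II only.

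**The concern.** A four-drug intensive regimen goes to up to 80 patients, and the plan holds its own mortality reference for the backbone. Yet nothing numeric in phase II responds to deaths as deaths. A trial with mostly fatal events and a trial with mostly reversible grade 3 events look identical to the rule if the counts match. Deaths recorded as hematological or as due to leukemia may not enter the count at all. At stake is how many patients are treated before excess mortality forces a decision: over 80 patients, 8% is 0.08 × 80 = 6.4 deaths and 25% is 0.25 × 80 = 20.

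**Working it through.** **1. Reproduce Table 4.** After each patient n with x events, stop if Pr(P > 0.30) > 0.90 under Beta(0.6 + x, 1.4 + n − x). N is 80, and an exact forward recursion over binomial paths gives the stopping probability. With the first look at patient 5, the rule stops 0.150, 0.351, 0.636 and 0.870 at 25%, 30%, 35% and 40%. Table 4 prints 0.15, 0.35, 0.63 and 0.88, so it is reproduced to within 0.01.

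The printed boundary list begins "7/13, 8/15, 9/18, 10/21" and shows nothing earlier. Taken literally it stops less often (0.065, 0.225, 0.517, 0.806). The list and Table 4 should be reconciled. The figures below use the version that matches Table 4, which is the more favourable to the plan.

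**2. Put deaths into that rule.** Table 4's rate is the total rate of counted events. Let d be the death rate, with all deaths counted, and o the rate of other grade 3 or higher non-hematological toxicity among the remaining patients. The total is d + (1 − d) × o. The documents give no value for o, so a range is assumed.

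| Deaths d | Other o | Total rate | Stops | Does not stop |
|---|---|---|---|---|
| 25% | 0% | 25% | 0.15 | 0.85 |
| 25% | 5% | 0.25 + 0.75 × 0.05 = 28.75% | 0.29 | 0.71 |
| 25% | 10% | 0.25 + 0.75 × 0.10 = 32.5% | 0.49 | 0.51 |
| 25% | 20% | 0.25 + 0.75 × 0.20 = 40% | 0.87 | 0.13 |
| 20% | 10% | 0.20 + 0.80 × 0.10 = 28% | 0.26 | 0.74 |
| 15% | 10% | 0.15 + 0.85 × 0.10 = 23.5% | 0.11 | 0.89 |

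If one death in five at d = 25% is not counted and there is no other toxicity, the counted rate is 20% and the rule fails to stop in 94.5% of trials.

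**3. What a death boundary would do.** Two illustrative rules follow the plan's convention of a prior with total weight 2 and its mean at the limit. Each stops if Pr(death rate > limit | data) > 0.95, from patient 5, N = 80. For a 10% limit the prior is Beta(0.2, 1.8); for a 15% limit it is Beta(0.3, 1.7).

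| True death rate | Stops, 10% limit | Stops, 15% limit |
|---|---|---|
| 8% | 0.07 | 0.02 |
| 15% | 0.56 | 0.18 |
| 20% | 0.89 | 0.52 |
| 25% | 0.99 | 0.84 |

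**4. Why the window matters for the limit.** Section 2.3 gives the 8% without a window or cause, and gives median survival of 34 weeks for the same study. Assuming a constant hazard, the proportion dead by day 56 (8 weeks) is 1 − 0.5^(8/34) = 0.15. The same formula, with a month taken as 30.4 days, gives about 0.21 for relapsed ALL (median 5.5 months, section 2.6). For AML after failure of hypomethylating agents (median 3.7 months, section 2.1) it gives about 0.29. These are rough figures, but all-cause 56-day death is clearly not the quantity that the 8% measures.

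**The case against.** A reader might infer from Table 4 that a 25% early-death rate passes in 85% of trials. The documents do not support that. The 25% row is total toxicity, so the figure requires every counted event to be fatal. It also covers all cycles rather than an early window, and it sets aside the other rules.

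The efficacy rules do matter. Response is assessed within 56 days, so a patient who dies before responding is a non-responder. In a simulation with 25% deaths, no other toxicity, the printed efficacy boundaries and the same response rate in both cohorts, only 28% of trials reach 80 patients when overall response is 30%. When it is 40%, 61% do. This protection depends on response falling. In the 60-patient AML cohort with response at the 40% target, 20% deaths and 10% other toxicity, the efficacy rule stops about 0.19. Table 2 gives that figure at 40% response whatever the mortality. Efficacy and toxicity rules together stop 0.36.

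It can also be said that deaths are reviewed. Section 5.2.1 does provide for that, so it would be wrong to call deaths unmonitored. But the provision has no threshold and stands only in the phase I text.

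The strongest objection is to the limit. A rule on all-cause 56-day death anchored on 8% could often stop a regimen no worse than the cited history: with the 10% limit it stops 0.56 at 15% mortality. That stands, and it determines how the limit should be set.

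A reader might also want aplasia added to the 30% rule. The documents give no aplasia rate, and a composite of two event classes would need its own limit and prior. Marrow sampling may also be omitted at very low white counts (section 6). The material supports no more than asking for the phase I and phase II definitions to be reconciled.

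**Conclusion.** The gap is real. Phase II has one numeric safety rule, it pools fatal and reversible non-hematological events under a 30% limit, and no boundary acts on death. Taken alone, the rule fails to stop at 25% deaths in about 85% of trials if deaths are the only counted events. That falls to about 51% with 10% other toxicity and about 13% with 20%. At 20% deaths plus 10% other toxicity it stops in about 26%.

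These sizes assume that all deaths are counted, that other toxicity occurs at the assumed rate among the remaining patients, and that looks begin at patient 5. Uncounted deaths make detection worse. The efficacy rules reduce the number of trials that run to 80, but they cannot stop a regimen that responds well and has excess mortality. The omission of aplasia from phase II is an inconsistency to reconcile; its effect cannot be sized from the documents.

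**What to change.** In section 11, add a continuous Bayesian boundary on early death for phase II:
- State the window and whether all deaths or only some causes count.
- The sponsor sets the limit from historical mortality over that same window and cause definition. The 8% induction figure should not be carried over to all-cause 56-day death.
- Print the prior, the boundary and a table of operating characteristics.
- Use the same death proportion and prior for the mortality rate under Analysis method.
- Say whether the review of deaths in section 5.2.1 also applies in phase II.
- Reconcile the phase I aplasia DLT with the phase II toxicity definition, stating how aplasia is followed in phase II. Do not add it to the unchanged 30% rule.

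The cost is protocol and SAP wording plus one more simulation. The statistical price is false stopping that depends on background mortality. With the illustrative 10% limit it is 0.07 at 8% mortality and 0.56 at 15%. With the 15% limit it is 0.02 and 0.18, while the rule still stops 0.84 at 25%. Both limits only show the trade-off; neither is a recommendation.

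### The toxicity stopping rule has no stated first look, and its wording, its boundary list and Table 4 imply three different ones

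*Combined protocol and SAP*

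**What the plan says.** The rule stands in section 11.2, under the heading on monitoring of non-hematological toxicities of grade 3 or higher. The toxicity probability P_E has a Beta(0.6, 1.4) prior. The wording is "we will stop the trial if, at any time during the study, we determine that there is more than 90% chance" that the rate exceeds 30%. No minimum number of patients is attached.

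A list of stopping pairs (toxicities/patients evaluated) follows. It begins "7/13, 8/15, 9/18, 10/21, 11/23, 12/26" and ends at 30/79.

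Table 4 then gives the early stopping probability and the median (quartiles) of the sample size: 0.15, 80 (80, 80) at true rate 0.25; 0.35, 80 (27, 80) at 0.30; 0.63, 42 (11, 80) at 0.35; and 0.88, 19 (7, 47) at 0.40.

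The rule pools both cohorts and covers toxicity "throughout all the cycles of treatment will also be closely monitored during the study for AML and ALL together". The maximum is 60 AML plus 20 ALL patients, so 80. The AML total is one "which includes 42 new patients and the 18 patients from phase I MTD level" (section 11, Phase II).

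**The concern.** A list whose first entry is at 13 patients cannot stop a quarter of trials by patient 7 or patient 11, yet Table 4 gives those as lower quartiles. The list is therefore incomplete, or the table describes some other rule. The verbal rule agrees with neither, because it can stop well before patient 5.

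This is the safety stopping rule for a four-drug regimen, so two people working from the same page could act differently on the same data. With 4 toxicities in 7 patients, the probability statement says stop and the list has no entry. Anyone judging the design by Table 4 would also think that the printed list stops a toxic regimen earlier than it does.

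**Working it through.** **Inputs (sections 11 and 11.2).** Prior Beta(0.6, 1.4); stop if Pr(P_E > 0.3 | data) > 0.90; N = 60 + 20 = 80.

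**Step 1: boundary.** After x toxicities in n patients, P_E follows Beta(0.6 + x, 1.4 + n − x). The boundary b(n) is the smallest x for which the tail above 0.3 exceeds 0.90. From patient 13 onward this reproduces all 24 printed pairs, so the prior, threshold and cutoff are not in doubt.

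Before patient 13 the same calculation gives:

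| x/n | Pr(P_E > 0.3) | Stop? |
|---|---|---|
| 1/1 | 0.789 | no |
| 2/2 | 0.928 | yes |
| 3/3 | 0.976 | yes |
| 3/4 | 0.935 | yes |
| 4/5 | 0.975 | yes |
| 4/7 | 0.901 | yes |
| 5/9 | 0.922 | yes |
| 6/12 | 0.905 | yes |
| 7/13 | 0.950 | yes (first printed pair) |

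The probability statement therefore also stops at 2/2, 3/3 to 3/4, 4/5 to 4/7, 5/8 to 5/9 and 6/10 to 6/12. None of these is listed.

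**Step 2: operating characteristics.** Let f_n(x) be the probability of x toxicities in n patients without an earlier stop. Then f_n(x) = (1 − p) f_{n−1}(x) + p f_{n−1}(x − 1). At each look, the mass at x ≥ b(n) is moved to a stop at n. This is exact. It assumes a look after every patient, with each listed count holding until the next pair.

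Early stopping probability by true rate:

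| Version | 0.25 | 0.30 | 0.35 | 0.40 |
|---|---|---|---|---|
| Table 4 as printed | 0.15 | 0.35 | 0.63 | 0.88 |
| First look at 5, 6 or 7 | 0.150 | 0.351 | 0.636 | 0.870 |
| Verbal rule, no minimum | 0.190 | 0.387 | 0.658 | 0.878 |
| Printed list, from 13 | 0.101 | 0.298 | 0.601 | 0.856 |

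Median (quartiles) of sample size:

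| Version | 0.25 | 0.30 | 0.35 | 0.40 |
|---|---|---|---|---|
| Table 4 as printed | 80 (80, 80) | 80 (27, 80) | 42 (11, 80) | 19 (7, 47) |
| First look at 5 | 80 (80, 80) | 80 (28, 80) | 40 (11, 80) | 19 (7, 48) |
| Verbal rule, no minimum | 80 (80, 80) | 80 (17, 80) | 34 (7, 80) | 16 (6, 45) |
| Printed list, from 13 | 80 (80, 80) | 80 (51, 80) | 53 (19, 80) | 25 (14, 54) |

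First looks at 5, 6 and 7 give the same stopping probabilities because 4 toxicities is the boundary at all three. A lower quartile of 7 at rate 0.40 needs at least 25% of trials to stop by patient 7. That probability is 0.29 with a first look at 5 to 7, and zero with a first look at 8 or later.

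**Step 3: size.** At rate 0.40, a first look at 5 stops 42% of trials by patient 12; the printed list stops none. Mean sample size, first look at 5 against the printed list, is 44.6 against 50.1 at rate 0.35 (difference 5.5) and 30.0 against 35.2 at 0.40 (difference 5.2).

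**Step 4: do the efficacy rules share the fault?** The AML and ALL rules also have no stated first look: their lists start at 8 patients, although their probability statements would stop from 0/1. Their tables do fit their lists. The AML list gives 0.906/0.725/0.504/0.318/0.187 against 0.91/0.73/0.51/0.33/0.19 in Table 2. The ALL list gives 0.852/0.703/0.537/0.383/0.255/0.159 against 0.85/0.7/0.54/0.38/0.26/0.16 in Table 3. The mismatch between list and table is confined to toxicity.

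**The case against.** **The probability statement governs, and the list only tabulates it.** On that reading 4/7 is a stop and there is no conflict of instruction. But the list is then incomplete, and Table 4 still does not match a rule without a minimum: its stopping probabilities are lower by 4.0, 3.7 and 2.8 points at 0.25, 0.30 and 0.35.

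**The start at 5 to 7 is inferred.** This is fair. A first look at 3 or 4 gives 0.165/0.365/0.645/0.873, within 2 points of Table 4. Its lower quartiles at 0.30 and 0.35 (22 and 9) and its medians at 0.35 and 0.40 (37 and 17) fit less well than those for 5 to 7. The number of simulated trials is not given; if it was about 1,000, a start at 3 or 4 is not firmly excluded. The contradiction does not depend on which is right, since no start at 13 can give quartiles of 7 and 11.

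**The list could be read only at the listed patient numbers.** That gives 0.065/0.225/0.517/0.806, further from Table 4.

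**Phase I already covers the early patients.** Much of this stands. Unless de-escalation occurs, the first 12 patients are phase I patients, under a rule that de-escalates above 30% DLT. At true rate 0.40, if every toxicity is also a DLT, no path reaching an unlisted pair at patients 5 to 12 escapes de-escalation by patient 12. If 75% or 50% of toxicities count as DLTs (an assumed range), about 4% or 23% of those paths escape, which is 1.6% or 9.8% of all trials. But a DLT is an event "occurring during the first course on study that meets any of the following criteria", and its consequence is de-escalation. The toxicity rule counts all cycles and stops the trial, so one does not replace the other.

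**Conclusion.** The concern holds. The list and Table 4 cannot describe the same rule, and the verbal rule matches neither. The individual pairs are correct; what is missing is the first look.

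The effect on overall stopping is modest: 0.02 to 0.03 at true rates 0.35 and 0.40, and about 0.05 at 0.25 and 0.30. The real difference lies in early stopping, with lower quartiles of 19 and 14 under the list against 11 and 7 in Table 4. The error does not run in one direction only, because Table 4 also overstates stopping at the acceptable rate of 0.25 (0.15 against 0.10).

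These figures assume a look after every patient, toxicity known at once, and list entries read as steps. Since the endpoint spans all cycles, real stopping would come later under every version. The point should be fixed; it does not undermine the design.

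**What to change.** State the minimum number of patients before the first toxicity look, attach it to the verbal rule, and make the list and Table 4 agree with it. Which first look was intended is for the sponsor to say.

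- **(a) First look at 5.** Add 4/5, 5/8 and 6/10 before 7/13 and keep Table 4, which this reproduces to within plausible simulation error. With a first look at 6 or 7, the first added pair would be 4/6 or 4/7. The stopping probability at 0.25 stays at 0.15.
- **(b) First look at 13.** Keep the list and replace Table 4 with stopping probabilities 0.10/0.30/0.60/0.86 and sample sizes 80 (80, 80), 80 (51, 80), 53 (19, 80) and 25 (14, 54). The stated performance at high toxicity becomes slightly less favourable.

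If no minimum was intended, the list must begin 2/2, 3/3, 4/5, 5/8, 6/10, and Table 4 must be replaced by the no-minimum figures above.

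The same sentence could state the first look at 8 that the AML and ALL lists already imply. The cost is one sentence plus a few pairs or a new table, with no extra patients and no change to endpoint, threshold or sample size.
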